## **11.2 PERMANENT TREATMENT DISCONTINUATION WITH INVESTIGATIONAL PRODUCT(S)**

Permanent treatment discontinuation is any treatment discontinuation associated with the definitive decision from the Investigator or the patient not to re-expose the patient to the IMP at any time.

### **11.2.1 List of criteria for definitive treatment discontinuation**

The patients may withdraw from treatment with IMP if they decide to do so, at any time and irrespective of the reason, or this may be the Investigator's decision. All efforts should be made to document the reasons for treatment discontinuation and this should be documented in the e-CRF.

Study drug will be permanently discontinued in case of the following events:

- Confirmed diagnosis of opportunistic infection based on the investigator's assessment following diagnostic workups and expert consultations
- Active tuberculosis:
  - the diagnosis can be made either on symptoms or on a chest radiograph suggestive of active TB. Patients should be referred to appropriate medical specialists and whenever possible, culture confirmation of disease should be obtained and recorded in the e-CRF.
- The patient is at risk through close contact with a person with active TB and the patient refuses to undergo TB evaluation.
- Culture positive for non-tuberculosis mycobacteria
- Symptoms of systemic hypersensitivity or anaphylactic reactions.
- Severe neurologic disease such as demyelinating disease or PML.
- Significant laboratory abnormalities:
  - ALT > 5xULN or ALT > 3xULN with concomitant total bilirubin > 2xULN (unless patient with documented Gilbert's syndrome)
  - neutrophil count < 500/mm^3, or neutrophil count < 1000/mm^3 with evidence of infection

- platelet count  $<50\,000/\text{mm}^3$ , or platelet count  $<100\,000/\text{mm}^3$  with evidence of bleeding (see [Section 10.2](#)).
- Conversion to HIV positive status
- Acute renal failure
- Pregnancy in female participant.
- Use of any biologic DMARDs other than IMP, or use of any JAK inhibitor
- For EFC13752 patients: use of any non-biologic DMARDs
- Any adverse events, per investigator judgment, that may jeopardize the patient safety.

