- Study drug must be temporarily discontinued; the patient must be assessed for evidence of infection and CBC blood test repeated within 48 hours from the study Investigator’s awareness of neutrophil count  $\geq 500/\text{mm}^3$  and  $< 1000/\text{mm}^3$ .
- Discontinuation of study drug is maintained until the neutrophil count returns to  $\geq 1000/\text{mm}^3$  ([Appendix L](#)).
- After the patient meets all requirements for resumption of study drug administration, including neutrophil count  $\geq 1000/\text{mm}^3$ , then study drug administration may resume **at the dose of 150 mg q2w**.

In case of a decrease in neutrophil count  $< 500/\text{mm}^3$  or if neutrophil count  $< 1000/\text{mm}^3$  and signs of infection:

- Study drug must be permanently discontinued.
- The patient must be assessed for evidence of infection and CBC blood test repeated within 48 hours from the study Investigator’s awareness of neutrophil count  $< 500/\text{mm}^3$ , or  $< 1000/\text{mm}^3$  and signs of infection.
- It is recommended to admit the patient to the hospital in case of neutrophil count  $< 1000/\text{mm}^3$  with suspicion of infection.
- Neutrophil count  $< 500/\text{mm}^3$  persisting for at least 5 days is to be reported as a serious adverse event.

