### 10.2.6 Platelets

Refer to [Section 10.5.4](#) criteria for reporting thrombocytopenia as AEPM/AESI with or without immediate notification.

For all patients, a CBC test must be performed a few days before or at Visit 3, but not earlier than the 12th day after the first dose of IMP administration (using either designated central lab or local laboratory facility), and results reviewed prior to the administration of the 2nd dose of study drug in order to confirm that the platelet count is not within the protocol-defined limits for temporary, or permanent discontinuation of study drug.

For all subsequent visits, in order to prevent the administration of study drug in patients at risk for thrombocytopenia, whenever the platelet count is below the LLN based on designated central laboratory test specifications, the CBC test must be **repeated** to confirm that the platelet count is not within the protocol-defined limits for temporary, or permanent discontinuation of study drug, before the next administration of study drug. The outlined procedures below will be followed:

- Contact patient as soon as possible and schedule “repeat CBC blood test”; the repeat blood test can be arranged using designated central lab or a local laboratory facility.
- If the results of the “repeat CBC blood test” (either designated central lab or local laboratory facility results) confirm that the platelet count is  $\geq 100,000/\text{mm}^3$  (100 GI/L), the study drug may be administered.
- If the results of the “repeat CBC blood test” (either designated central lab or local laboratory facility results) demonstrate that the platelet count is below  $100,000/\text{mm}^3$  (100 GI/L), the study drug must be temporarily or permanently discontinued, per protocol stopping rules defined below, and in [Appendix L](#).
- Note: All per protocol-scheduled CBC tests must be performed using designated central lab, even in circumstances when a local laboratory facility is also used to determine the platelet count before dosing.

In case of a decrease in platelet count to a level  $\geq 50,000/\text{mm}^3$  and  $< 100,000/\text{mm}^3$ :

- Study drug must be temporarily discontinued; the patient must be assessed for evidence of spontaneous bleeding, and CBC blood test repeated within 48 hours from the study Investigator’s awareness of platelet count  $\geq 50,000/\text{mm}^3$  and  $< 100,000/\text{mm}^3$ .

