- Discontinuation of study drug is maintained until the platelet count returns to  $\geq 100,000/\text{mm}^3$  (see [Appendix L](#)).
- After the patient meets all requirements for resumption of study drug administration, including platelet count  $\geq 100,000/\text{mm}^3$ , then study drug administration may resume **at the dose of 150 mg q2w**.

The study drug must be permanently discontinued if platelet count is  $< 50,000/\text{mm}^3$  or if  $< 100,000/\text{mm}^3$  with spontaneous bleeding (see [Appendix L](#)).

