### 11.1 TEMPORARY TREATMENT DISCONTINUATION WITH INVESTIGATIONAL PRODUCT(S)

Temporary treatment discontinuation may be considered by the Investigator because of suspected AEs eg, suspected malignancy or because of abnormal laboratory values.

The following is a list of criteria for temporary discontinuation. This list is not exhaustive and IMP may be temporarily discontinued for additional reasons based on Investigator judgment:

- Increase in ALT level  $\geq 3$  x ULN to  $\leq 5$  x ULN and bilirubin  $\leq 2$  x ULN (unless the patient has documented Gilbert's disease). The IMP can be resumed at the dose of 150 mg q2w only after the ALT has returned to a value  $< 3$  ULN and all requirements for resumption of study drug administration are met (see [Section 10.2.4](#) and [Appendix L](#)).
- Decrease in neutrophil count to a level between 500/mm^3 to  $< 1000$ /mm^3 without signs and symptoms of a potential infection. The IMP can be resumed at the dose of 150 mg q2w only after the neutrophils have returned to a value  $\geq 1000$ /mm^3 and all requirements for resumption of study drug administration are met (see [Section 10.2.5](#) and [Appendix L](#)).
- Decrease in platelet count to between 50 000 cells/mm^3 to  $< 100$  000 cells/mm^3 without spontaneous bleeding. The IMP can be resumed at the dose of 150 mg q2w only after the platelet count is  $\geq 100$  000/mm^3 and all requirements for resumption of study drug administration are met (See [Section 10.2.6](#) and [Appendix L](#)).
- Infections requiring oral or parenteral treatment with antibacterial, antiviral and/or antifungal agents (See [Section 10.2.1](#) for additional guidance)
- Surgery requiring temporary treatment discontinuation of biologic DMARD as per applicable guidelines

If the dose is reduced to 150 mg q2w the reduced dose will be maintained for the whole duration of the treatment period.

The IMP can be temporarily discontinued for  $\leq 59$  days (3 IMP doses can be missed).

Reinitiation of treatment with the IMP will be done under close and appropriate clinical/and or laboratory monitoring.

If the restart of the IMP occurs later than 38 days since the last IMP dose (2 IMP doses were already missed), the IMP has to be administered at the study site and the patient to be observed for 30 minutes for any medical events.

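### For platelets of 50,000 to <100,000/mm³, Protocol 11.2.1 makes the stop permanent on any bleeding, while 10.2.6 and 11.1 make it permanent only on spontaneous bleeding

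*Protocol*

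**What the plan says.** Three Protocol sections govern a platelet count of 50,000 to <100,000/mm³.

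- **10.2.6 (Platelets)** requires a temporary stop in this band and says that "the patient must be assessed for evidence of spontaneous bleeding". The stop becomes permanent below 50,000/mm³, or below 100,000/mm³ "with spontaneous bleeding".
- **11.1 (temporary discontinuation)** lists this band as a temporary stop "without spontaneous bleeding. The IMP can be resumed at the dose of 150 mg q2w only after the platelet count is" at least 100,000/mm³ and the other requirements for restarting are met.
- **11.2.1 (definitive discontinuation)** lists a count below 50,000/mm³, or below 100,000/mm³ "with evidence of bleeding", among the events for which the drug will be permanently stopped. The bullet ends with a pointer to Section 10.2.

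Sections 10.2.6 and 11.1 also refer to Appendix L, whose content is not shown in the text available for this review. Section 11.2.1 does not cite it.

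For neutrophils of 500 to <1000/mm³, the permanent trigger is "and signs of infection" in 10.2.5 and "with evidence of infection" in 11.2.1. Section 11.1 keeps the stop temporary "without signs and symptoms of a potential infection".

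**The concern.** The word spontaneous separates temporary from permanent in 10.2.6 and 11.1, and it is missing from 11.2.1. Both instructions are mandatory in form, so investigator judgment does not resolve them. Two sites could handle the same patient differently, each following the protocol.

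Four things depend on the classification:

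- **Treatment.** One reading allows resumption at the reduced dose, kept for the rest of the treatment period (11.1). The other ends treatment.
- **Notification.** Under 10.5.4, thrombocytopenia leading to permanent discontinuation must be notified within 24 hours; without permanent discontinuation it is reported routinely. This matters only when the event is not otherwise serious, because a serious event is expedited either way.
- **Analysis.** The SAP counts discontinuations by reason and dose reductions (2.2), TEAEs leading to discontinuation (2.4.4.1), and time to dose reduction and time from reduction to discontinuation (2.4.3). Safety is the primary objective.
- **Entry.** Exclusion criterion E 14 refers to the protocol's permanent-discontinuation criteria, so the conflict also reaches eligibility.

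**Working it through.** No arithmetic applies. The check sets the wordings side by side and classifies the same test patients under each section.

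**Cut-offs.** The numbers agree wherever they appear: 50,000 and 100,000/mm³ for platelets, 500 and 1000/mm³ for neutrophils. Any conflict must come from the bleeding or infection qualifier.

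**Platelets**

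| Test patient | 10.2.6 | 11.1 | 11.2.1 | Result |
|---|---|---|---|---|
| 50,000 to <100,000, no bleeding | temporary | temporary | not listed | consistent |
| 50,000 to <100,000, spontaneous bleeding | permanent | outside the platelet criterion | permanent | consistent |
| 50,000 to <100,000, non-spontaneous bleeding (e.g. trauma) | temporary | temporary | permanent | **conflict** |
| <50,000 | permanent | outside the platelet criterion | permanent | consistent |

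One row of four conflicts. In it, 10.2.6 and 11.1 agree with each other and 11.2.1 stands alone.

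**Neutrophils, 500 to <1000/mm³**

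| Test patient | 10.2.5 | 11.1 | 11.2.1 | Result |
|---|---|---|---|---|
| No infection | temporary | temporary | not listed | consistent |
| Clinical signs of infection | permanent | outside the neutrophil criterion | permanent on an ordinary reading | consistent |
| Symptoms only, or laboratory or imaging findings only | depends on the term | depends on the term | depends on the term | unclear |

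The last row diverges only if signs, signs and symptoms of a potential infection, and evidence are read as three separate thresholds. The protocol does not define them so. Section 10.2.5 mixes the terms itself: in the band and again at the permanent stop it says that "the patient must be assessed for evidence of infection", while the permanent trigger is worded "and signs of infection".

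**Effect on AESI counts.** SAP 2.1.3.1, Table 1 flags thrombocytopenia by a standardised MedDRA query, not by the reporting route. Protocol 10.5.4 lists thrombocytopenia both with and without permanent discontinuation. The category count is therefore the same under either reading. What can move is the row for TEAEs leading to discontinuation inside that category's display (SAP 2.4.4.1).

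**The case against.** The best defence is that 11.2.1 is a summary list. Its platelet bullet points to Section 10.2, and 10.2.6 asks for an assessment for evidence of spontaneous bleeding, so the shorter phrase in 11.2.1 may be an abbreviation of it. That is a plausible account of how the difference arose. It does not remove the conflict: the pointer leads to different wording without saying which governs, and 11.2.1 is the list a site would consult for a permanent stop. Appendix L might settle the term, but 11.2.1 does not refer to it and its content cannot be read here.

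It is also fair to say that surgery is a weak example. For joint replacement the drug is already interrupted beforehand and restarted after wound healing (8.9). Bleeding after trauma is the cleaner case.

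A reader might infer more than the documents support:

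- *That the neutrophil rules contradict each other in the same way.* All three wordings make the stop permanent with infection and temporary without it. Section 10.2.5 requires a temporary stop across the whole 500 to <1000/mm³ band while infection is assessed, and the 11.1 list says that it is not exhaustive. A patient with possible but unproven infection is therefore not left without a rule. This is ambiguity at the edge.
- *That all three sections use different bleeding triggers.* Sections 10.2.6 and 11.1 match.
- *That AESI counts depend on the section read.* The category counts do not, for the reason shown in the working.

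**Conclusion.** The platelet conflict is real and narrow. For a count of 50,000 to <100,000/mm³ with non-spontaneous bleeding, 10.2.6 and 11.1 give a temporary stop and 11.2.1 gives a permanent one. The conclusion rests on reading 11.2.1 as written and on nothing in the visible text ranking one section above another.

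The documents give no frequency for this combination, so its size cannot be stated; it may be a handful of patients or none. The point merits correction because it concerns mandatory stopping rules in a study whose primary objective is safety, not because it is likely to move the overall results. The neutrophil wording is a minor matter of harmonisation. No view is taken on which clinical rule is right.

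**What to change.** Reconcile Protocol 10.2.6, 11.1 and 11.2.1 so that a single bleeding qualifier defines the boundary between temporary and permanent discontinuation, with no patient in both lists. Check that Appendix L says the same. The sponsor's clinical team must choose the qualifier.

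In the same amendment, use one infection term for neutrophils below 1000/mm³ in 10.2.5, 11.1 and 11.2.1.

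The cost is clarification wording in the next amendment. The planned SAP summaries can stay as they are, since they take the recorded classification as input.

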### **11.2.2 Handling of patients after permanent treatment discontinuation**

Patients will be followed up according to the study procedures as specified in this protocol up to the scheduled date of study completion, or up to recovery or stabilization of any AE to be followed-up as specified in this protocol, whichever comes last:

- If possible, and after the permanent discontinuation of treatment, the patients will be assessed using the procedures normally planned for the end of treatment visit and the follow up visit 6 weeks later.

All permanent treatment discontinuation should be recorded by the Investigator in the appropriate pages when considered as confirmed.

### **11.3 PROCEDURE AND CONSEQUENCE FOR PATIENT WITHDRAWAL FROM STUDY**

The patients may withdraw from the study, before study completion if they decide to do so, at any time and irrespective of the reason:

- If possible, the patients are assessed using the procedure normally planned for the end-of treatment visit and post treatment safety follow-up visit.

For patients who fail to return to the site, the Investigator should make the best effort to re-contact the patient (eg, contacting patient's family or private physician, review available registries or health care database), and to determine his/her health status, including at least his/her vital status. Attempts to contact such patients must be documented in the patient's records (eg, times and dates of attempted telephone contact, receipt for sending a registered letter).

Patients who have withdrawn from the study cannot be enrolled again (treated) in the study. Their inclusion and treatment number must not be re-used.

## 12 STUDY PROCEDURES

### 12.1 VISIT SCHEDULE

It is preferred that all study visits take place in the morning. Some visits that include only scheduled blood sampling (V3, V5, V6.1) (Week 2, Week 6, and Week 10) can be scheduled as Home Visits or clinic visits.

Patients will be considered as having completed their treatment per protocol and should complete the end of treatment visit (EOT):

- At Week 264, if sarilumab has been commercialized in their country at that time. EOT visit should be performed instead of Week 264 visit and the assessments defined in the flowchart ([Section 1.2.1](#), [Section 1.2.2](#)) should be completed.
- At any visit after Week 264 once sarilumab is commercialized in their country (applicable for patients in the countries where commercial sarilumab is not available at the time the patients completed their Week 264). Some of the assessments are NOT required at EOT for these patients; please refer to the flowchart ([Section 1.2.1](#), [Section 1.2.2](#)) for details.
  - When commercialization occurs in a given country, investigators in that country will be alerted by the Sponsor and they will inform their patients during the next scheduled study visit that their subsequent visit 12 weeks later will be the EOT visit.
- At any visit after Week 264 at the time the study is closed in 2020 in countries where commercialization has still not occurred. Some of the assessments are NOT required at EOT for these patients; please refer to the flowchart ([Section 1.2.1](#), [Section 1.2.2](#)) for details.
  - EOT visits for all patients remaining in the study at that time will occur at scheduled clinic visits over a 3-month period in order to stagger the completion of EOT visits across the study, and allow the completion of the 6-week follow up period for all patients prior to study closure. Investigators will be alerted by the Sponsor that the study closure is approaching and they will inform their patients during the next scheduled study visit that their subsequent visit 12 weeks later will be the EOT visit.
- At Week 264, for patients in the UK no matter when the sarilumab is commercially available in the country. EOT visit should be performed instead of Week 264 visit and assessments defined in the flowchart ([Section 1.2.1](#), [Section 1.2.2](#)) should be completed.

If a patient is permanently and prematurely discontinued from treatment, all assessments planned at the end of treatment visit (EOT) should be performed. Some assessments at EOT are not required if the EOT visit occurs after Week 264, as indicated in the flowchart.

The safety follow-up visit should be performed six weeks from the end of treatment for all patients including those who discontinued before the planned end of treatment with the following exception:

- In patients who complete sarilumab treatment per protocol in countries where sarilumab is commercially available the post treatment follow-up visit may be cancelled if the patient initiates treatment with commercial sarilumab during the post treatment follow-up period. However, in this case, a telephone contact must be established with the patient to capture all AEs occurring up to the 1st administration of commercial sarilumab.

From Week 24 (Visit 8) onwards, some patients may participate in the PFS-S sub-study. No details of the sub-study assessments are described in this section. Please refer to the [Appendix R](#) for all information related to the sub-study assessments for these patients.

### **12.1.1 Visit 1: Screening Visit (D-7 to D-1)**

**A Screening Visit will only be completed by patients enrolling in the LTS11210 study from ACT11575 or EFC11072 Part A and Part B Cohort 1.**

A specific written informed consent form (WICF) should be signed and dated to enter the LTS11210 prior to any screening assessment.

The majority of the screening assessments and labs procedures for this study correspond to the last treatment visit in the study EFC11072 or ACT11575.

The patient will be proposed to enter this study if eligible. If not eligible or unwilling to enter this long term study then he or she will have a follow-up visit 6 weeks after the completion of the study EFC11072 or ACT11575.

**The following items will then be checked and recorded:**

Assess eligibility by review of inclusion/exclusion criteria.

- Prior and current medication dosage to confirm inclusion and exclusion criteria.
- Previous medical and surgical history: record only new medical and surgical history that has occurred since the randomization visit in study EFC11072, or ACT11575
- Record demographic information.
- History of alcohol and illicit drug use and smoking history.
- For patients entering LTS11210 from Part A of EFC11072 or ACT11575, complete SF-36 questionnaire.

**The following will be obtained from the End of Treatment visit in the study EFC11072 or ACT11575:**

- Perform a physical examination.
- Record vital signs including body temperature, blood pressure and Heart Rate.
- Record body weight (kg).
- (Fasting) blood for clinical laboratory determinations including hematology, clinical chemistry profile, LFTs and lipids.

- Obtain urine for urinalysis (dipstick) for: specific gravity, pH, glucose, blood, ketones, proteins, bilirubin, urobilinogen, nitrate, leukocytes. If positive for proteins, microscopic analysis will be performed by central laboratory.
- Obtain urine for pregnancy test if female of child bearing potential.
- Obtain 12 – lead ECG
- Perform tuberculosis assessments
- Perform a complete joint examination to assess tender and swollen joints
- Ask the patient to complete relevant questionnaires: HAQ, patient’s global assessment, patient’s pain questionnaire.
- Ask the patient to complete a sleep questionnaire, the FACIT-Fatigue, WPAI, and for EFC11072 Part B patients, the SF-36.
- Complete the physician global assessment.
- Obtain blood sample for acute phase reactants: hs-CRP. The investigator, patient and sponsor will be blind to the results of the hs-CRP at screening and at baseline. The investigator is advised not to do a local CRP testing unless needed for safety reasons.
- Obtain blood sample for PK (sarilumab), Serum IL-6, and anti-sarilumab antibody.
- Obtain serum sample for future biomarker tests
- ANA (if ANA titer is >1:160 obtain Anti-ds DNA).
- X-rays of hand and feet (applicable to patients who completed EFC11072 Part B

